### 5.5. Additional analyses and sensitivity analyses

As this is a feasibility trial, no sensitivity analyses will be undertaken.

### 5.6. Harms

All harms that have been collected shall be reported as a total number that have occurred in the duration of the trial, and then reported by group on an as-treated basis.

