# 3. Assessment and management of risk

### 3.1. Potential risks

As the patient population is made up of people living with dementia, they may lack the capacity to give informed consent and therefore be considered vulnerable.

Page 17 of 59

The intervention is comprised of physical activity which could result in injuries being sustained.

Patient participants will undertake the intervention at their home without medical assistance available if injuries occur, such as if the participant falls.

There is the potential impact of increased burden on both the patient participant and the carer participant when taking part in this study compared to usual care.

Visits from research support workers and therapists to the patient participants home introduce the risk of COVID-19 infection during these home visits.

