	A score of 14 or more seconds has been shown to indicate high risk of falls.	
Goal Attainment Scaling (GAS) (intervention only)	As part of the intervention, therapists will set individualised goals with participants. The goals will be agreed with the PWD by the therapists at the initial assessment and assigned 'weights'. GAS is a method of scoring the extent to which these goals are achieved in a way that is standardised for analysis [21, 22]. Progress towards goals will be measured at the final intervention visit, allowing a numerical score to be calculated at 6 months.	Baseline, 6 months
	Each goal is rated on a 5-point scale, with the degree of attainment captured for each goal area: If the patient achieves the expected level, this is scored at 0. If they achieve a better than expected outcome this is scored at: +1 (somewhat better)	
	+2 (much better)	
	If they achieve a worse than expected outcome this is scored at:	
	-1 (somewhat worse) or	
	-2 (much worse)	
	Goals may be weighted to take account of the relative importance of the goal to the individual, and/or the anticipated difficulty of achieving it.	
	Normally 3-4 goals are identified, which are incorporated into the single GAS score.	
	Overall Goal Attainment Scores are then calculated by applying a formula:	
	Overall GAS = 50 + $\frac{10 \Sigma(w_{i} x_{i})}{\sqrt{(0.7 \Sigma w_{i}^{2} + 0.3(\Sigma w_{i})^{2})}}$ Where:	
	wi = the weight assigned to the i th goal (if equal weights, wi = 1)	
	xi = the numerical value achieved (between -2 and + 2)	
	A simple spreadsheet calculator is available for use.	
Cognition assessed with mini ACE (Mini-ACE)	The Mini-ACE consists of 5 items and has a maximum score of 30	Baseline
Falls diary	Number of falls will be assessed through prospective completion of a diary during the 6 months of follow-up. Aid of an unpaid carer can be utilised if required. For each day, participants will be asked to record if they had any falls and, if so, explain the context and consequences of the fall. The data from the falls diary will be used to calculate the proportion of participants with one or more falls and the fall rate per person per year.	During the 6 months of follow up

Secondary		
Carer participants		

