#### 7.8. Quantitative assessment of falls

PWD will be asked to complete a prospective falls diary for the duration of the six month follow up period with the aid of an unpaid carer if required. These will be used to calculate:

Page 36 of 59

- the fall rate per person per year
- the proportion of participants with one or more falls
- injury and fracture rates

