#### Adverse events (AE)

Non-serious AEs will not be recorded or reported for the study. The components of the intervention are not novel and safety of the intervention is not an outcome measure.

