**Table 16- Frequency of Falls Assessed Using the Falls Diary**

Patient Health Related Quality of Life Outcomes	Maintain Group			Control Group			Model Statistics	
	N	Mean	SD	N	Mean	SD	IRR	95% CI
Falls Diary at 28 Weeks								

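### The planned final analysis does not separately identify harm from the intervention, and the SAP omits the injury and fracture rates that the protocol says the diaries will supply

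*SAP*

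**What the plan says.** Protocol 3.1 states the risk in two parts: "The intervention is comprised of physical activity which could result in injuries being sustained", and the activity takes place at home "without medical assistance available if injuries occur, such as if the participant falls".

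Three kinds of relevant data are collected:
- **Falls diary.** Protocol 4.5 (Table 2) says that each day "participants will be asked to record if they had any falls and, if so, explain the context and consequences of the fall". Protocol 7.8 lists what the diaries will be used to calculate: an annualised fall rate, the share of participants who fell at least once, and "injury and fracture rates". Protocol 10.1 has the diary data entered in the study database.
- **Serious events.** Under Protocol 8.3, deaths from any cause and admissions for a fall, a fracture or a musculoskeletal injury are recorded, and the site PI or a delegate assesses causality. For lesser events the rule is "Non-serious AEs will not be recorded or reported for the study".
- **Session records.** Protocol 8.1.3 and 12.5 describe a form completed at each visit.

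The SAP's harms analysis is one sentence in 5.6: "All harms that have been collected shall be reported as a total number that have occurred in the duration of the trial", then by group as treated. SAP 3.3 requires at least one session for a person to count in the intervention group. None of the 20 shell tables is a harms table. Table 16 has a single row, "Falls Diary at 28 Weeks", with N, mean, SD and an incidence rate ratio.

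**The concern.** The harm that the protocol singles out is a fall or injury while doing the programme. Nothing in the planned final report would show how many people had one.

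A total of harms can be the same in both groups when its content differs. Four admissions in one person and four deaths in four people both count as four. Relatedness, which the PI has already judged, would not be shown.

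A fall during prescribed activity that does not lead to admission or death is not an adverse event record. It can appear only in the overall falls count, mixed with background falls in a population chosen because it falls. A rate ratio near 1 could then reflect extra falls during activity offset by fewer falls at other times.

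This matters for what the pilot is meant to feed. Objective D is to refine the intervention for the full trial, and none of the progression criteria in Protocol 4.4 concerns safety. The final report of harms and falls is therefore a main safety input to that work.

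**Working it through.** The plan states no figure for harms, so there is none to reproduce. The check sets the passages side by side and adds one calculation of scale.

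**1. What is collected against what is reported.**

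| Information | Collected | In the SAP |
|---|---|---|
| Death or admission, as event type | Protocol 8.3 | Not separated in 5.6 |
| PI causality | Protocol 8.3, 8.4 | Not mentioned |
| Participants affected, as distinct from events | Derivable from the event records | Not specified |
| Number of falls | Diary | Table 16 |
| Share who fell at least once | Diary; Protocol 4.5 and 7.8 | No row in Table 16 |
| Injury and fracture rates | Diary; Protocol 7.8 | Absent |
| Context of each fall | Diary; Protocol 4.5 | Not used |

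**2. Whether the SAP brings in the missing measures by reference.** SAP 5.1 defers to Protocol Table 2 for how outcomes are calculated. The diary entry in Table 2 covers the share who fell and the fall rate, but not injuries or fractures. Those rates stand only in Protocol 7.8, so the cross-reference does not reach them.

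**3. How small session time is within follow-up.** Inputs: at most 22 sessions including boosters, 60 minutes each (Protocol 8.1.3; I assume that boosters last the same), and 26 weeks from the start of the intervention (Protocol 7.7).
- Session time: 22 × 1 h = 22 h.
- Follow-up: 26 × 168 h = 4,368 h.
- Share: 22 / 4,368 = 0.50%.
- With 16 waking hours a day (an assumption): 22 / (26 × 7 × 16) = 22 / 2,912 = 0.76%.
- Adding the two assessment visits at an assumed hour each: 24 / 4,368 = 0.55%.

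Prescribed activity between visits adds exposure that the documents do not quantify. On any of these figures, an undivided count consists mainly of time outside sessions.

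**4. What a participant-level figure could support.** Suppose none of the 30 planned intervention participants has a diary fall placed during a session or prescribed activity. The exact upper limit for zero events is 1 − a^(1/n).
- One-sided 95%: 1 − 0.05^(1/30) = 9.5%.
- Two-sided 95%: 1 − 0.025^(1/30) = 11.6%.
- With the plan's ICC of 0.05 and 10 per cluster, the design effect is 1 + 9 × 0.05 = 1.45 and the effective n is 30 / 1.45 = 20.7. The one-sided limit becomes 13.5%, and the two-sided limit 1 − 0.025^(1/20.7) = 16.3%.

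These limits are wide, and they assume that such falls are written in the diary. They are still more than the plan would report. I give no per-session figure, for the reason stated in the objection.

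**The case against.** The strongest reply is that the protocol made a deliberate choice. Section 8.3 calls the trial low risk, says that the components are not novel, and states that safety is not an outcome. Serious events are overseen in other ways: related ones go to the trials unit and then the sponsor within 24 hours each, related deaths go to the TSC and REC within 7 days, and the TSC reviews the data for patterns (Protocol 8.3, 8.4). Table 16 already compares net falls between arms, and a count of activity-related falls in one arm has no comparator. Deaths before follow-up would ordinarily appear among the reasons for loss in the CONSORT diagram (SAP 4.3).

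Much of this stands. It rules out three stronger readings that a reader might infer:
- **That intervention harm is never reported.** A fall during the intervention that leads to admission or death is in the 5.6 total, and Protocol 7.8 itself plans injury and fracture rates. The gap is that such harm is not separately identified.
- **That the session forms already capture falls, so a rate per visit could be given.** Protocol 8.1.3 describes activities, recommendations and adherence. Protocol 12.5 describes planned and actual activities and obstacles to delivery. Neither names falls or injuries, so no fall on those forms would not mean that no fall occurred.
- **That the protocol describes unsupervised exercise.** Section 3.1 speaks of the absence of medical help, not of supervision.

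Part of the gap, the non-recording of non-serious events, is a protocol decision and not an SAP choice.

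The reply does not dispose of the point. The SAP has a harms section and a safety population, so what it reports should be interpretable. Oversight during the trial does not specify the final report and does not cover falls without admission. A descriptive count needs no comparator to inform refinement.

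**Conclusion.** The point holds as a reporting gap in the SAP. Followed as written, 5.6 yields a count overall and by group that does not distinguish deaths from admissions, people from events, or related from unrelated. Table 16 ignores the recorded context and consequences of falls, and the injury and fracture rates in Protocol 7.8 have no place in the SAP.

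The feasibility estimates and the progression decision rules are unaffected. What is lost is a safety description that the existing records can largely provide, for activity whose scheduled sessions occupy about 0.5% of follow-up time.

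Two assumptions limit this. Diary context must be complete enough to classify most falls, which the documents do not show. The safety text must also be current: SAP section 6 cites protocol version 5.0, while the protocol available is version 3.0, so the recording rules in force could differ.

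**What to change.** Amend SAP 5.6 and add one harms table in three parts.

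1. **Both arms, serious events.** Put deaths and admissions for a fall, a fracture or a musculoskeletal injury on separate rows. For each, give participants with at least one event over the number in the group (as defined in SAP 3.3), the number of events, and PI relatedness.
2. **Both arms, diary measures.** Report the share who fell at least once and the injury and fracture rates, as Protocol 7.8 provides. Keep the Table 16 rate ratio as the comparative falls outcome.
3. **Intervention arm, descriptive.** Report the number of participants with at least one fall that the diary context places during a session or prescribed activity, with an exact 95% CI, and the number of falls that cannot be classified. Define the coding rule before the diaries are read. Use the session forms only if they are confirmed to record falls, and give no rate per session otherwise.

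Check the wording against protocol version 5.0 before finalising.

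The cost is a paragraph, a table and the coding of free text from about 60 diaries at the planned sample size. The downside is that context and consequences are reported by the participant or carer and may be incomplete, which the unclassifiable count makes visible. No change to clinical management or to the adverse event recording rules is proposed.

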### 5.7. Statistical software

The latest available version of STATA at the time of analysis will be used for all trial analyses. At time of writing, this is STATA 18.5.

## 6. Related Documents

Relevant Documents held in the Trial Master File:

- Protocol Version 5.0, Implemented on 22nd May 2024
- Data Management Plan Version 1.0
- Randomisation Requirements Version 1.0

## 8. Appendices

**Table 1- Patient Demographics 1**

Patient Demographics	Control Group		Maintain Group	
	N	n (%)	N	n (%)
Dementia Subtype				
Alzheimer’s Disease				
Vascular Dementia				
Mixed Dementia				
Dementia with Lewy Bodies				
Parkinson’s Disease Dementia				
Frontotemporal Dementia				
Unspecified Dementia				
Other				
Ethnicity				
White				
Mixed/Multiple Ethnic Groups				
Asian/Asian British				
Black/African/Caribbean/Black British				
Other				
Sex				
Male				
Female				
Residence Type				
Private Home				
Sheltered Accommodation				
Other				
Living Arrangement				
Lives Alone				
Lives with Spouse/Partner				
Lives with Other Family Member				
Lives with Someone Other than Family				
Other				
Does the Participant Speak/Read and Understand English?				
Yes				
No				
Highest Education Level				
Secondary School or Equivalent				
Sixth Form/College/Apprenticeship				
University Undergraduate				
University Postgraduate				
Smoking Status				
Never Smoked				
Ex-Smoker				
Current Smoker				

**Table 2- Patient Demographics 2**

Patient Demographics	Control Group			Maintain Group		
	N	Mean	SD	N	Mean	S.D
Age						
Number of Falls in the last 6 Months						

Table 3- Carer Demographics 1

Carer Demographics	Control Group			Maintain Group		
	N	Mean	SD	N	Mean	S.D
Age						

Table 4- Carer Demographics 2

Carer Demographics	Control Group		Maintain Group	
	N	n (%)	N	n (%)
How Often does Carer Typically See Patient				
Every Day				
Most Days				
Once a Week				
Less than Once a Week				
Relationship to Patient				
Spouse/Partner				
Son/Daughter				
Grandchild				
Sibling				
Other Family Member				
Friend				
Other				
Ethnicity				
White				
Mixed/Multiple Ethnic Groups				
Asian/Asian British				
Black/African/Caribbean/Black British				
Other				
Sex				
Male				
Female				

Table 5- Stop/Go Criteria Outcomes

Screening/Eligibility Feasibility Outcomes	N	n (%)
Proportion of Eligible Patients Consenting to Pilot Trial		

Proportion of Participants who Attend <math>\geq 60\%</math> of Sessions as Planned.		
Proportion of consented participants retained for key outcome data at week 28		

**Table 6- Screening Demographics 1**

Screening Demographics	N	n (%)
Ethnicity		
White		
Mixed/Multiple Ethnic Groups		
Asian/Asian British		
Black/African/Caribbean/Black British		
Other		
Sex		
Male		
Female		

**Table 7- Screening Demographics 2**

Screening Demographics	N	Mean	SD	Min	Max
Age					

**Table 8- Cognition Assessed with Mini ACE**

	Control Group			Maintain Group		
Mini-Ace Outcomes	N	Mean	SD	N	Mean	SD
Cognition assessed with Mini-Ace at Baseline						

**Table 9- Clinical Baseline Characteristics**

Clinical Baseline Characteristics	N	Mean	SD	Min	Max
Clinical Frailty Score at Baseline					

**Table 10- Charleston Co-Morbidity Index**

Charleston Co-Morbidity Index	N	n (%)

Myocardial infarction		
Congestive heart failure		
Peripheral vascular disease		
Cerebrovascular accident or transient ischemic attack		
COPD		
Connective tissue disease		
Peptic ulcer disease		
Liver disease		
Diabetes mellitus		
Hemiplegia		
Moderate to severe chronic kidney disease		
Solid tumour		
Leukaemia		
Lymphoma		
AIDS		

**Table 11- Activities of Daily Living (ADL) Measured with the Disability Assessment for Dementia (DAD)**

Disability Assessment for Dementia Outcomes	Maintain Group			Control Group			Model Statistics	
	N	Mean	SD	N	Mean	SD	Mean Difference	95% CI
ADL assessed with the DAD at Baseline								
ADL assessed with the DAD at 28 Weeks								

**Table 12- Mobility Assessed using the Timed Up and Go (TUG)**

Timed Up and Go Outcomes	Maintain Group			Control Group			Model Statistics	
	N	Mean	SD	N	Mean	SD	Mean Difference	95% CI
Mobility assessed with the TUG at Baseline								
Mobility assessed with the TUG at 28 Weeks								

**Table 13- Patient Health Related Quality of Life (HRQL) assessed with the EQ-5D-5L and EQ-5D-5L Proxy**

Patient Health Related Quality of Life Outcomes	Maintain Group			Control Group			Model Statistics	
	N	Mean	SD	N	Mean	SD	Mean Difference	95% CI
HRQL assessed with EQ-5D-5L at Baseline								
HRQL assessed with EQ-5D-5L at 28 Weeks								
HRQL assessed with EQ-5D-5L Proxy at Baseline								
HRQL assessed with EQ-5D-5L Proxy at 28 Weeks								

**Table 14- Patient Health Related Quality of Life assessed with the QoL-AD and QoL-AD Proxy**

Patient Health Related Quality of Life Outcomes	Maintain Group			Control Group			Model Statistics	
	N	Mean	SD	N	Mean	SD	Mean Difference	95% CI
HRQL assessed with QoL-AD at Baseline								
HRQL assessed with QoL-AD at 28 Weeks								
HRQL assessed with QoL-AD Proxy at Baseline								
HRQL assessed with QoL-AD Proxy at 28 Weeks								

**Table 15- Psychological Consequences of Falling Using the Short-FES-I**

Patient Health Related Quality of Life Outcomes	Maintain Group			Control Group			Model Statistics	
	N	Mean	SD	N	Mean	SD	Mean Difference	95% CI
Short-FES-I at Baseline								
Short-FES-I at 28 Weeks								

**Table 16- Frequency of Falls Assessed Using the Falls Diary**

Patient Health Related Quality of Life Outcomes	Maintain Group			Control Group			Model Statistics	
	N	Mean	SD	N	Mean	SD	IRR	95% CI
Falls Diary at 28 Weeks								

**Table 17- Carer burden assessed with the Zarit burden interview 12 (ZBI-12)**

Carer Burden Outcomes	Maintain Group			Control Group			Model Statistics	
	N	Mean	SD	N	Mean	SD	Mean Difference	95% CI
Carer Burden assessed with ZBI-12 at Baseline								
Carer Burden assessed with ZBI-12 at 28 Weeks								

**Table 18- Carer quality of life assessed with the EQ-5D-5L**

Carer Health Related Quality of Life Outcomes	Maintain Group			Control Group			Model Statistics	
	N	Mean	SD	N	Mean	SD	Mean Difference	95% CI
HRQL assessed with EQ-5D-5L at Baseline								
HRQL assessed with EQ-5D-5L at 28 Weeks								

**Table 19- Goal Attainment Scale (Maintain Group Only)**

	N	Mean	SD
Goal Attainment Scale at Baseline			
Goal Attainment Scale at 12 Weeks			
Goal Attainment Scale at 28 Weeks			

**Table 20- Proportion of Follow-Ups Occurring Within Window**

	Maintain Group		Control Group	
	N	n (%)	N	n (%)
Deviations- Timing of Visits				
Proportion of Follow-Ups Occurring Within Allowed Window at Final Follow-Up				

For all tables:

N = Total Number of Responses (Denominator)

n = Number whom the given option applied to (Numerator)

SD = Standard Deviation

IRR = Incident-Rate Ratio
